4. OBJECTIVES*

The Specific Aims for Phase 2 have been modified from the original submission with approval from the program officer at NIDA. Updated Aims are as follows:

Phase 1, Aim 1: To develop the OARS+CM platform. User-centered design principles will be employed to enhance the existing OARS software to produce OARS+CM. This will culminate in a proof-of-concept study of up to 20 individuals with OUD and their providers/clinicians whose feedback and experiences will be used to iteratively improve the interface and features. The usability criterion will be reached when \geq 3 participants in a row are able to use the program without staff assistance (with on-device support if needed, as intended) and no more substantive improvements are needed. We will also assess acceptability, and rates of treatment initiation and adherence (attending therapy, drug urine/saliva tests).

Phase 2, Aim 1: To assess the efficacy of OARS+CM in promoting MOUD treatment initiation. Using a randomized controlled trial (N=102 randomized), the efficacy of the OARS+CM (n=51) in promoting MAT initiation will be tested against TAU with MyMAT (an educational mobile app) (n=51).

H1: OARS+CM will result in greater MOUD treatment initiation from acute care settings than TAU with MyMAT.

Phase 2, Aim 2: To assess efficacy of OARS+CM in promoting transition from MOUD Initiation to maintenance.

H2: OARS+CM will result in greater rates of sustained abstinence for 6 months after the index visit.

H3: MOUD therapy attendance will be increased such that OARS+CM >TAU with MyMAT.

Phase 2, Aim 3: To evaluate costs. Exploratory data on cost-effectiveness, cost avoidance and cost savings through reduced acute care visits between conditions will be collected and analyzed.

This submission is currently seeking approval for Phase 2 following successful completion of Phase 1, as the NIH will only fund Phase 2 if Phase 1 is successful. All materials for Phase 2 in this submission outline what has occurred since Phase 1 was completed successfully. Any changes to Phase 2 material have been revised and are being submitted to the IRB as a modification for review and approval when appropriate.

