6. INCLUSION AND EXCLUSION CRITERIA*

Inclusion and Exclusion Criteria: See grant: "HUMAN PARTICIPANTS PROTECTION" (p.17) for details. The Overall Study Design, Study Population and Randomization, and Interventions for Phase 2 have been modified from the original submission. Updated Overall Study Design, Study Population and Randomization, and Interventions are as follows:

Overall Study Design: This Fast-Track STTR includes a small proof of concept pilot study followed by a randomized controlled trial (RCT) with two conditions: 1) treatment as usual (TAU) with MyMAT, and 2) the OARS + CM. This study will use recruitment and study enrollment procedures successful in our prior SUD research (refer to Biosketches). Participants will be individuals with OUD presenting to acute care settings. They will complete a screening survey to assess for minimal eligibility criteria and confirm their interest. Once confirmed, research staff will obtain written informed consent and enrolled in the study. Participants will be randomized to one of two conditions described above. The study period begins at enrollment during their index acute care visit. Follow-up surveys and tracking through the mobile application (OARS+CM) and review of all relevant healthcare records will occur at 1, 3, and 6 months after enrollment. For scientific rigor, biochemical verification of abstinence from opioids

will be obtained from outpatient treatment records. Self-reported use will also be obtained through structured follow-up assessments.

Study Population and Randomization: We will randomly assign N=102 individuals with OUD meeting minimal eligibility criteria to one of two conditions using REDCap, allocated 1:1 to the two conditions.

Interventions:

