11. PROCEDURES INVOLVED*

Measures: For Phase 1, the System Usability Scale (SUS) (patients and clinicians), Timeline Followback (TLFB) (patients only), and Addiction Severity Index (ASI) (patients only) will be used and is included in this submission. For Phase 2, The Mini Quiz (MQ), Mini-Usability Acceptability Testing (Mini-UAT) questionnaire, Timeline Followback (TLFB), PROMIS Pain Intensity and Interference Scales (PIIS), HIV Risk Behavioral Scale (HRBS), Post-traumatic Stress Diagnostic Scale for DSM-5 (PDS), Treatment Satisfaction Scale (TSS), and the System Usability Scale (SUS) will be used and are included in this submission.

Assessments/Procedures for Phase 2	Intake	Onboarding	Transition to Suboxone	Week 1 to 12	Month 1	Month 3 / End of Tx	Month 6
Mini Quiz, Patient form, OUD	X						
Mini-UAT, Service Utilization, TLFB	X				Х	Х	Х
PIIS, HRBS, PDS, U-Tox	X				Х	Х	Х
Healthcare Utilization	X						Х
App training, warm hand-off scheduling outpatient Suboxone intake		Х					
Monitor completion of MOUD intake			Х				
MOUD TAU / OARS+CM				Х			
Monitor treatment attendance/u-tox				X			
Treatment satisfaction, SUS*						Х	

^{*}Only for OAR+CM group

Phase 1: Aim 1 (Develop OARSCM): 30 Clinicians (20 user testing, 10 dyads) and 30 Patients

- 1a. After the OARSCM is developed, patients meeting criteria and consenting to participate will be guided through using the mobile application on their personal smartphone. If the participant's smartphone is not available for use to complete the instructed tasks, the participant will be able to use a study-provided iPad.
- 1b. Clinicians not associated with a specific patient participant verbally consenting to participate after reviewing the User Testing Fact Sheet will be guided through using the provider portal using a test account on a study provided computer in a private office.
- 1c. Clinicians working at the UMass Bridge Clinic, at the CleanSlate Addiction Treatment Center at SaVida Health, and at Spectrum Health Systems associated with a patient participant (considered a dyad) verbally consenting to participate after reviewing the Dyad Fact Sheet will receive an in-person or virtual training on the provider portal on a study provided computer in a private office. After the training, the clinician will provide standard MAT treatment to patient participants and use the OARSCM provider portal to track treatment.

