- 4. Participants will receive a welcome call at 1-week post-enrollment. This call will welcome participants to the study and provide an opportunity to answer any questions they may have about participation as well as ensure they are not having any issues with study mobile applications. This call will take about 5 minutes.
- 5. They will complete 3 follow-up telephone calls to find out how they are doing. The calls will focus on their substance use, especially opioid use, treatment engagement, healthcare visits, health, and well-being. These calls will take about 20 30 minutes to complete. The calls will occur at 1, 3, and 6 months after the enrollment date.
- 6. The researchers will review the participants' healthcare records, including the Massachusetts Prescription Monitoring Program's EHR-integrated tool MassPAT that provides information on participant's prescriptions for MOUD through the 6 months after enrollment. We will review the

healthcare record for all participants and will only be viewing the MassPAT record for participants who do not have urine toxicity results at their outpatient MOUD provider at the 1, 3, and 6-month follow up time points. MassPAT will be used to determine if a participant is still engaging in treatment during these follow-up time points if the participant cannot be reached for their follow-up interviews or if they have stopped attending appointments at their study clinic site and have not requested to leave the study.

- 7. We will be seeking to collect information from medical providers or records outside of the UMMS system (a substance use treatment provider in the community that doesn't have a UMMS connection) and will require a signature on a Release of Medical Information with designated treatment facilities identified
- 8. The researchers will review publicly available databases, like the participants' state's vital statistics registry (a document created by the state that tracks important health indicators, like births, deaths, and cause of death). See grant: "RESEARCH STRATEGY" (p.8-13) for details.

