Sample size justification. We use the proportion of participants who complete the Suboxone intake to start treatment as the calculating indicator. Based on the findings from a large randomized clinical trial on MAT treatment for opioid dependence after an acute care visit,¹⁵⁸ we estimate the proportion of patients who will initiate MAT at baseline is about 35%. We hypothesize that OARS will increase the rate by 25% and OARS+CM will increase the rate by 50%. Using G-Power program (proportions procedure) with $\alpha=0.05$, $N=150$ (50 each group), the calculated statistical power is >0.80 for the comparisons between TAU and OARS, TAU and OARS+CM, and OARS and OARS+CM.

Aim 2 is to assess the efficacy of OARS+CM for increasing Suboxone treatment adherence and abstinence outcomes. Main outcomes will be the percentage of opioid-free urine toxicology tests, and the percentage of group/individual therapy sessions attended. Secondary outcomes will be the longest duration of abstinence (LDA) outcome, measured at month 1, month 3 (end of study period) and month 6 (end of follow-up period), and sustained abstinence from Suboxone start through each follow-up. LDA and sustained abstinence will be as a composite of the greatest number of days with consecutive negative urine samples and self-reported no use; a composite of biochemical evidence and subjective report is needed because urine tests are too infrequent in the clinical setting to rigorously determine sustained abstinence based solely on biochemical evidence. Sustained abstinence and LDA are usually non-normally distributed and will be examined accordingly. We will assess the effect of the intervention using linear mixed model, controlling for the dependence of repeated measures and the clustering effects.

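### Sustained abstinence is counted from Suboxone start in the SAP but from the index visit in H2, and the SAP gives no score to participants who never start

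*SAP*

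**What the plan says.** Protocol section 4 (Objectives) states H2 as "OARS+CM will result in greater rates of sustained abstinence for 6 months after the index visit". The aim above it reads "To assess efficacy of OARS+CM in promoting transition from MOUD Initiation to maintenance". Section 6 (Overall Study Design) opens the study period at enrollment, during the index acute care visit. Section 11 (Procedures Involved, Phase 2 item 5) times follow-up the same way: "The calls will occur at 1, 3, and 6 months after the enrollment date".

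The SAP, under Aim 2, lists two secondary abstinence outcomes: longest duration of abstinence (LDA) and "sustained abstinence from Suboxone start through each follow-up". It describes both as a composite count of consecutive days, built from negative urine samples and self-reported non-use, and assigns them a linear mixed model. Under Statistical Design and Power, and again under Phase 2, RCT, it says the intent-to-treat sample will be analysed.

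Self-report does not depend on being in treatment. Section 6 says "Self-reported use will also be obtained through structured follow-up assessments", and the section 11 assessment table schedules the row "Mini-UAT, Service Utilization, TLFB" at intake and at months 1, 3 and 6.

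**The concern.** H2 compares the randomised conditions over a period that begins on the same footing for everyone. The SAP outcome has the same end points but a start that each participant sets by entering treatment. Entry into treatment happens after randomisation and is what the intervention is meant to change.

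Three things follow:

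- The SAP outcome is not the H2 outcome.
- Someone who never starts has no day from which to count, and no scoring rule is given. If such people are left out, the arms are compared among participants selected on the Aim 1 outcome. Any gain from bringing more people into treatment is then lost from the H2 comparison.
- The length of the window differs between participants according to when they start.

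**Working it through.** **1. Time origins side by side**

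| | Start of window | End of window |
|---|---|---|
| H2, Protocol section 4 | Index visit (enrollment) | 6 months later |
| SAP, Aim 2 | Suboxone start | Each follow-up, timed from enrollment |

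The ends agree at month 6 and the starts do not. The SAP's statement that mixed models use all available data by maximum likelihood does not help, because it cannot define an outcome that has no start date.

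**2. Planning rates**

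The SAP gives no design figure for this outcome. Its only figure is power above 0.80 for treatment initiation, with 50 per group in three groups. The inputs are 35% under TAU and increases of 25% (OARS) and 50% (OARS+CM), without saying whether these are relative or in percentage points. I used the pooled normal approximation,

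power = Φ[(|p1 − p2|·√n − z·√(2·p̄·(1 − p̄))) / √(p1(1 − p1) + p2(1 − p2))], with n = 50 and α = 0.05.

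Results are in the order TAU v OARS, TAU v OARS+CM, OARS v OARS+CM:

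- Percentage points (35/60/85%): one-sided 0.81, >0.99, 0.89; two-sided 0.71, >0.99, 0.81.
- Relative (35/43.75/52.5%): one-sided 0.23, 0.55, 0.22; two-sided 0.14, 0.42, 0.14.

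The stated figure is reproduced only with percentage points and a one-sided test. That favours 85% as the intended OARS+CM rate, but the text does not settle it, so both readings are carried.

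**3. Participants with no start date**

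I take a completed intake as Suboxone start. The number with no start date in an arm is 51 × (1 − p).

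- TAU: 51 × 0.65 = 33.2
- OARS+CM, relative reading (35% × 1.5 = 52.5%): 51 × 0.475 = 24.2
- OARS+CM, absolute reading (35% + 50 points = 85%): 51 × 0.15 = 7.7

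Across both arms this is 57.4 of 102 (56%) or 40.8 of 102 (40%), unevenly split.

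**4. Window length to month 6**

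Take month 6 as day 182. Days in the window = 182 − start day. H2 requires 182.

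- Day 2 (the 48-hour target in Protocol section 5): 180
- Day 60: 122 (122/182 = 67%)
- Day 120: 62 (62/182 = 34%)

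The later start days are illustrations, since the documents give no distribution of start times. With month 1 as day 30, a start after day 30 leaves no month-1 window. If the outcome is pass/fail, a late starter needs fewer abstinent days than H2 asks. If it is the day count that the SAP also describes, a late start caps the score.

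**5. Why the scoring of non-starters matters (assumed values)**

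Let s be the proportion sustained among starters and q among non-starters, equal in both arms, so the app has no effect once treatment begins. The starters-only difference is 0. Over all randomised, the rate in an arm is p·s + (1 − p)·q, and the difference is (pC − 0.35)(s − q), where pC is OARS+CM initiation.

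- s = 0.30, q = 0: 10.5% v 15.75% (+5.25 points) or 25.5% (+15.0)
- s = 0.30, q = 0.10: 17.0% v 20.5% (+3.5) or 27.0% (+10.0)
- Over s = 0.20–0.50 and q = 0–0.10: from 0.175 × 0.10 = +1.75 to 0.50 × 0.50 = +25.0 points

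These differences are the Aim 1 effect carried through, not extra abstinence on treatment.

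**The case against.** The best defence is that Aim 2 is about moving from initiation to maintenance, so counting from initiation is a natural choice, and the outcome is only secondary in the SAP. Both statements are correct. They justify keeping the from-start analysis, but they do not make it an answer to H2, which names the index visit.

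Several stronger readings are tempting, and the documents do not support them:

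- **That the SAP restricts this analysis to starters.** No such rule is written. Under the intent-to-treat statement a non-starter could be scored as not sustained or as zero days. What can be said is that no score is stated.
- **That late starters always face an easier target.** This holds only for a pass/fail outcome. The SAP's day-count wording and linear model point the other way, while H2 speaks of rates.
- **That LDA has the same fault.** LDA needs no Suboxone start. The SAP calls month 3 the end of the study period, and the protocol opens that period at enrollment, so LDA can be read as starting there. It is not said outright.
- **That correcting this needs no new data.** The documents give no look-back for the Timeline Followback (TLFB). If it is shorter than the gap between calls, some days are not covered.
- **That the main Aim 2 outcomes are wrong too.** The SAP says "Main outcomes will be the percentage of opioid-free urine toxicology tests, and the percentage of group/individual therapy sessions attended" and the supplied text gives no denominator, but Protocol section 10 refers endpoints to grant pages that were not supplied. That is a point to clarify. So are the section 5 schedule of 4 + 2 + 1 = 7 visits beside 12 tests and 12 sessions, and the urine toxicology row beside telephone follow-up in section 11.

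**Conclusion.** The mismatch in time origin is plain on the text and should be corrected. As written, the SAP's sustained-abstinence outcome does not test H2, and it leaves never-starters without a start date or a stated score.

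The size rests on the SAP's planning rates, which come from a three-arm calculation that no longer matches the two-arm design. True initiation may differ. The counts would then change, but the gap remains at any initiation below 100%. The window effect is small for participants seen within 48 hours and grows with delay. The percentage-point differences in step 5 depend on assumed abstinence rates and show only how much the scoring choice can matter; they do not estimate bias in this trial.

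A reader might infer that the trial's primary result is at risk. It is not: the Aim 1 outcomes do not use this definition.

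**What to change.** In the SAP:

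- Define sustained abstinence from the index visit for all 102 randomised, using TLFB at months 1, 3 and 6 plus any urine result.
- State whether the outcome is a rate, as in H2, or a number of days, and match the model to it.
- State how participants who never start, and those with neither self-report nor urine, are scored.
- Confirm that the TLFB look-back covers every day between contacts.
- If use before intake is not to count, set a grace period in days from the index visit, the same in both arms.
- Name the same origin for LDA.
- Keep the from-Suboxone-start version as a supportive analysis labelled as among starters.
- Report the all-randomised result beside Aim 1, because it includes the initiation effect.

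The cost is mainly wording, plus a change to the TLFB interview if its look-back proves too short. There are two downsides. Abstinence in non-starters may rest on self-report alone, and without a grace period any use between the visit and intake counts against the participant.

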Aim 3 is to evaluate costs. Economic evaluation of the CM intervention is highly relevant to considerations of implementation and will be informed by expert guidelines.¹⁵⁹ The primary hypothesis is that the incremental cost-effectiveness (cost per participant who does not have repeat OUD-related emergency acute care, measured at the end of treatment and the last follow-up) will be acceptable and support sustainability. The study will also determine the incremental cost of the CM intervention per OUD patient treated, to identify the budget impact of adoption on a large-scale basis if the intervention is efficacious. For analyses, we will determine the Incremental Cost Effectiveness Ratio (ICER) in dollars per repeat acute care visit averted. This ratio is the difference in cost incurred by the OARS+CM group divided by the difference in the proportion of participants without repeat acute care services over the short (intervention period) and long term (last follow-up). The statistical uncertainty of the incremental cost-effectiveness will be estimated by bootstrap analysis of trial data, a method that preserves the covariance between costs and outcomes.¹⁶⁰ A cost-effectiveness acceptability curve will be plotted with the proportion of replicates that are cost-effective at different threshold values of willingness to pay per successful quit participant.¹⁶¹ The p -value for the statistical test that the OARS+CM intervention is cost-effective will be found by determining the proportion of replicates that are above each threshold value. We will conduct a literature review of cost-effectiveness studies to identify likely threshold values of dollars per OUD person treated in general. Costs of activities that are solely for research purposes (weekly surveys, follow-ups) will be excluded. Also see the Commercialization Plan for our approach to cost-savings and cost-avoidance.

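### Aim 3 labels its cost-effectiveness ratio per visit averted but computes it per participant, and states its thresholds in two further units

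*SAP*

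**What the plan says.** All the relevant text is in the Aim 3 paragraph of the SAP. In order, it gives:

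- **Hypothesis:** the incremental cost-effectiveness, expressed as "cost per participant who does not have repeat OUD-related emergency acute care", will be acceptable.
- **Budget impact:** a separate quantity, the "incremental cost of the CM intervention per OUD patient treated, to identify the budget impact".
- **ICER label:** the ratio is stated "in dollars per repeat acute care visit averted".
- **ICER formula:** the cost difference is "divided by the difference in the proportion of participants without repeat acute care services".
- **Acceptability curve:** it plots "the proportion of replicates that are cost-effective at different threshold values" of "willingness to pay per successful quit participant".
- **p-value:** it "will be found by determining the proportion of replicates that are above each threshold value".
- **Source of thresholds:** a literature review of cost-effectiveness studies is to identify likely "threshold values of dollars per OUD person treated in general".

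The protocol (section 4, Objectives, Phase 2 Aim 3) describes the cost data as exploratory and attaches no hypothesis to them.

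**The concern.** A cost-effectiveness ratio can be compared with a willingness-to-pay value only when both are in dollars per unit of the same effect. The Aim 3 paragraph uses a participant unit in the hypothesis and formula, a visit unit in the label, a quitting unit on the curve, and a treated-person unit for the literature thresholds. It gives no conversion between them.

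Two things are at stake. First, a per-participant figure would be published as a per-visit figure, and whenever people have more than one repeat visit the two can differ by a multiple. Second, the conclusion on whether the intervention is cost-effective, and its p-value, depend on which threshold is chosen. If the threshold unit is open, it can be settled after the results are known, and a threshold taken in either stated unit belongs to a different outcome from the one in the hypothesis.

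**Working it through.** The documents contain no ICER, cost, repeat-care rate, visit count or threshold value, so there is no figure to reproduce. The check is a comparison of units, followed by an illustration on assumed inputs.

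**Step 1. Units side by side**

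| Element | Effect unit |
|---|---|
| Hypothesis | participant without repeat OUD-related emergency acute care |
| ICER denominator | participant without repeat acute care |
| ICER label | repeat acute care visit averted |
| Acceptability curve | participant who successfully quits |
| Literature thresholds | OUD person treated |

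The hypothesis and the denominator agree on the participant. The other three do not match them. The word quit appears nowhere else in either document; the nearest outcome, sustained abstinence, belongs to Aim 2.

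**Step 2. When label and formula agree**

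Let P0 be the share with no repeat care and m the mean number of repeat visits per participant.

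- As written: ICER = cost difference / (P0 in OARS+CM − P0 in TAU).
- As labelled: ICER = cost difference / (m in TAU − m in OARS+CM).

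These are equal only if the difference in mean visits equals the difference in the share with any repeat visit, for example when nobody has more than one.

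**Step 3. Illustration (all inputs assumed)**

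Take P0 = 0.60 in TAU and 0.70 in OARS+CM, with an extra cost of $400 per participant.

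As written: 400 / (0.70 − 0.60) = $4,000 per additional participant without repeat care.

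Per visit averted, with m derived from P0. Poisson: m = −ln P0. Negative binomial with dispersion k: m = k(P0^(−1/k) − 1).

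| Visit model | m, TAU | m, OARS+CM | Visits averted per participant | Dollars per visit averted |
|---|---|---|---|---|
| At most one visit each | 0.400 | 0.300 | 0.100 | 4,000 |
| Poisson | 0.511 | 0.357 | 0.154 | 2,595 |
| Negative binomial, k = 1 | 0.667 | 0.429 | 0.238 | 1,680 |
| Negative binomial, k = 0.5 | 0.889 | 0.520 | 0.368 | 1,086 |

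Dollar figures use unrounded means. One additional participant without repeat care therefore corresponds to 1.00, 1.54, 2.38 or 3.68 visits averted.

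This range is not a bound. If repeat users average 2 visits in TAU and 3 in OARS+CM, the visit difference is 0.40 × 2 − 0.30 × 3 = −0.10. The per-visit ratio is then 400 / (−0.10) = −$4,000, while the per-participant ratio is still +$4,000.

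**Step 4. The replicate rule**

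The p-value sentence counts replicates above each threshold without saying what is compared. Suppose a replicate has $400 extra cost and an effect 10 points worse. Its ratio is 400 / (−0.10) = −$4,000, which is not above a threshold of $5,000, so a bare ratio comparison would count it as favourable. Its incremental net benefit is 5,000 × (−0.10) − 400 = −$900, which correctly counts against the intervention. If the plan means position relative to the willingness-to-pay line, the second calculation is already what it does.

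**The case against.** The strongest defence is that the formula governs. The sentence after the label defines the ratio exactly, and it matches the hypothesis on the participant unit. An analyst who follows it computes the right kind of quantity, and relabelling the horizontal axis does not move an acceptability curve. This stands. A reader might infer that the curve and p-value are computed on the wrong effect; the documents do not support that. The error is confined to the reported unit and to the unit in which a threshold is chosen or read.

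A second tempting inference is that the denominator measures a broader outcome than the hypothesis, because it omits the OUD-related and emergency qualifiers. The text does not establish this. Under the eligibility table (protocol section 6) the index visit must be for opioid-related complaints, so repeat acute care can reasonably be shorthand for another such visit. The same table does include inpatient units and community partners as well as emergency departments, so the wording still needs settling.

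A third is that the p-value rule favours the intervention. That follows only if the rule is coded as ratio above threshold. The SAP permits this coding but does not require it, and the preceding sentence already speaks of replicates being cost-effective, which fits the sound reading.

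It can also be said that the per-person-treated wording belongs to the budget-impact result. However, that sentence seeks threshold values from cost-effectiveness studies and directly follows the threshold test, so it reads as supplying that test. What exactly it means per person treated is not settled by the text.

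Finally, Aim 3 is exploratory in the protocol. This limits the importance of the point but does not remove it, since the SAP gives Aim 3 a primary hypothesis and a p-value.

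**Conclusion.** The point holds in a limited form. As written, a per-participant ratio would be reported as a per-visit ratio, and the willingness-to-pay and literature thresholds are in units that are not the ratio's own, one of them undefined. The computed ratio and curve can stand. A threshold read or tested in the stated units would not address the Aim 3 hypothesis.

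The size cannot be derived from the documents. Under the assumed inputs, $4,000 per participant corresponds to between $4,000 (no one with more than one repeat visit) and about $1,086 per visit averted (negative binomial, k = 0.5), and arms that differ in visits per repeat user can fall outside that range. The difference in wording between hypothesis and denominator may be shorthand. The replicate rule is a request for clarification, not a demonstrated error. Aims 1 and 2, the sample size and the power are unaffected. The change should be made because it is cheap and removes a choice that could otherwise be made after the results are seen.

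**What to change.** 1. Relabel the ICER as dollars per additional participant without repeat OUD-related emergency acute care. Use that outcome in the hypothesis, denominator, acceptability curve and thresholds, and remove the reference to quitting.
2. Before any between-arm outcome data are seen, decide whether the records can classify visits as OUD-related emergency care. If they cannot, use all repeat acute care in every one of those places.
3. Express thresholds in dollars per such participant. If no published threshold exists in that unit, show the curve over a stated dollar range without a threshold test.
4. Keep cost per OUD patient treated as the budget-impact result only.
5. If cost per visit averted is also wanted, divide by the between-arm difference in mean visits per participant.
6. Classify each bootstrap replicate by incremental net benefit = threshold × effect difference − cost difference. Plot the share above zero, and take the one-sided p as the share at or below zero. This changes nothing if the plan already means the willingness-to-pay line.

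The cost is a few words in the SAP and a few lines of code on the same bootstrap. Protocol section 11 lists utilization measures, calls about healthcare visits and record review, but does not say that visits are classified as OUD-related or emergency, so the preferred outcome may need that extra step. Published thresholds in this unit may not exist, in which case the threshold test is lost and only the curve remains.
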